8.4.5 Pregnancy test

All pre-menopausal women who are not surgically sterile will have urine pregnancy testing and serum pregnancy test at screening as per [Table 8-1](#).

If the result of urine pregnancy test is positive, the patient must not be randomized and the result confirmed by the serum pregnancy test result. If the result of the serum pregnancy test is positive, the participant must be considered as a screen failure.

A positive pregnancy test during the study requires immediate discontinuation from study drug. The participant must be followed to understand the outcome of the pregnancy. Refer to [Section 10.1.4](#) for details on pregnancy reporting.

8.4.6 Appropriateness of safety measurements

The safety assessments selected are appropriate for this protocol, which utilizes a marketed compound where the safety profile has been established. The assessments are relevant to the critical care setting and will enable determination of therapeutic response in this setting.

8.5 Additional assessments

8.5.1 Unscheduled assessments

In the case of clinically significant abnormalities, safety concerns required repeat testing or if additional assessments need to be performed, information should be reported in the relevant CRF page using the Unscheduled visit pages.

8.5.2 Assessments pre and post hospital discharge

In the case that a participant is discharged from hospital during the study, the following guidelines must be followed:

- If the participant is discharge prior to Day 10, assessments for Day 10/early discharge visit should be completed prior to discharge
- If the participant continues treatment up to Day 10 at home, guidelines in [Section 6.1.3](#) should be followed. The site must contact the participant to assess compliance, and report any dose interruptions and stop dates of treatment, adverse events and relevant concomitant medications in the CRF
- Day 15 and Day 40 visits may be performed via phone call, an onsite visit is not mandated, at a minimum COVID-19 participant status, adverse events and relevant concomitant medications, and study completion status (as applicable) must be assessed.
- In the case that the participant is still hospitalized for either or both Day 15 and Day 40 visits additional assessments requested in [Table 8-1](#) if assessed, as per local practices, may be reported in the relevant CRF pages.

8.5.3 Biomarkers

Serum and plasma will be stored for future biomarker analysis and will be covered by the secondary data use informed consent provided at time of screening.

Sample(s) will be collected at the time point(s) defined in the Assessment Schedule ([Table 8-1](#)) when possible.

Follow instructions for sample collection, numbering, processing, and shipment provided in the laboratory manual.

9 Study discontinuation and completion

9.1 Discontinuation and completion

9.1.1 Study treatment discontinuation and study discontinuation

Discontinuation of study treatment for a participant occurs when study treatment is stopped earlier than the protocol planned duration and can be initiated by either the participant or the investigator. The investigator must discontinue study treatment for a given participant if, he/she believes that continuation would negatively impact the participant's well-being.

If, for any reason, one of the study drugs should be stopped prior to day 5, then the both study drugs should be discontinued and the reason for discontinuation reported in the CRF.

Study treatment must be discontinued under the following circumstances:

- Participant/guardian decision
- Pregnancy
- Use of prohibited treatment as per recommendations in the prohibited treatment section
- Any situation in which study participation might result in a safety risk to the participant including cardiac events (please refer to [Section 10.2](#) and [Section 16](#) for additional safety monitoring criteria)
- Following emergency unblinding
- Unsatisfactory therapeutic effect
- Any laboratory abnormalities that in the judgment of the investigator, taking into consideration the participant's overall status, prevents the participant from continuing participation in the study

If discontinuation of study treatment occurs, the investigator should record the primary reason for the participant's premature discontinuation.

Participants who discontinue study treatment or who decide they do not wish to participate in the study further should NOT be considered withdrawn from the study UNLESS they withdraw their consent (see 'Withdrawal of Informed Consent' section). **Where possible, they should be assessed as per visit schedule in [Table 8-1](#).**

After study treatment discontinuation, at a minimum, in abbreviated visits, the following data should be collected at clinic visits or via telephone/email contact:

- New / concomitant treatments
- Adverse Events / Serious Adverse Events

The investigator must also contact the IRT to register the participant's discontinuation from study treatment.

If discontinuation occurs because treatment code has been broken, please refer to Emergency breaking of treatment code section.

9.1.2 Withdrawal of informed consent

Participants may voluntarily withdraw consent to participate in the study for any reason at any time. Withdrawal of consent occurs only when a participant:

- Does not want to participate in the study anymore,
- and
- Does not want any further visits or assessments
- and
- Does not want any further study related contacts

In this situation, the investigator should make a reasonable effort to understand the primary reason for the participant's decision to withdraw his/her consent and record this information.

Where consent to the use of personal and coded data is not required, participant therefore cannot withdraw consent. They still retain the right to object to the further use of personal data.

Study treatment must be discontinued and no further assessments conducted, and the data that would have been collected at subsequent visits will be considered missing.

Further attempts to contact the participant are not allowed unless safety findings require communicating or follow-up.

All efforts should be made to complete the assessments prior to study discontinuation. A final evaluation at the time of the participant's study discontinuation should be made as detailed in the assessment table.

Novartis/Sponsor will continue to retain and use all research results (data) that have already been collected for the study evaluation.

9.1.3 Lost to follow-up

For participants whose status is unclear because they fail to appear for study visits without stating an intention to discontinue or withdraw, the investigator must show "due diligence" by documenting in the source documents steps taken to contact the participant, e.g. dates of telephone calls, registered letters, etc. A participant should not be considered as lost to follow-up until due diligence has been completed or until the end of the study.

9.1.4 Early study termination by the sponsor

The study can be terminated at any time for any reason by Novartis. Should this be necessary, the participant should be seen as soon as possible and treated as a prematurely withdrawn participant. Adverse events and laboratory findings will be continually reviewed during the study. New enrollment and/or dosing for a treatment arm or study overall may be paused in case of safety concerns that are suspected to be related to study drug, including:

- > 2 participants with Torsade de Pointes or Ventricular Tachycardia **associated with** QTcF > 500 msec and QTcF prolongation > 60 msec

The investigator may be informed of additional procedures to be followed in order to ensure that adequate consideration is given to the protection of the participant's interests. The investigator will be responsible for informing the Institutional Review Board/Independent Ethics Committee (IRBs/IECs) of the early termination of the trial.

9.2 Study completion and post-study treatment

Study completion is defined as when the last participant finishes their Study Completion visit and any repeat assessments associated with this visit have been documented and followed-up appropriately by the Investigator or, in the event of an early study termination decision, the date of that decision (e.g. Each participant will be required to complete the study in its entirety and thereafter no further study treatment will be made available to them).

All randomized and/or treated participants should have a safety follow-up call conducted 30 days after last administration of study treatment. The information collected is kept as source documentation. All SAEs reported during this time period must be reported as described in [Section 10.1.3](#). Documentation of attempts to contact the participant should be recorded in the source documentation.

There is no planned post-study-treatment in this study.

10 Safety monitoring and reporting

10.1 Definition of adverse events and reporting requirements

10.1.1 Adverse events

An adverse event (AE) is any untoward medical occurrence (e.g. any unfavorable and unintended sign [including abnormal laboratory findings], symptom or disease) in a clinical investigation participant after providing informed consent for participation in the study. Therefore, an AE may or may not be temporally or causally associated with the use of a medicinal (investigational) product.

The investigator has the responsibility for managing the safety of individual participant and identifying adverse events.

Novartis qualified medical personnel will be readily available to advise on trial related medical questions or problems.

The occurrence of adverse events must be sought by non-directive questioning of the participant at each visit during the study. Adverse events also may be detected when they are volunteered by the participant during or between visits or through physical examination findings, laboratory test findings, or other assessments.

Adverse events must be recorded under the signs, symptoms, or diagnosis associated with them, accompanied by the following information (as far as possible) (if the event is serious refer to [Section 10.1.2](#)):

1. The severity grade:
 - mild: usually transient in nature and generally not interfering with normal activities
 - moderate: sufficiently discomforting to interfere with normal activities
 - severe: prevents normal activities
2. Its relationship to the study treatment. If the event is due to lack of efficacy or progression of underlying illness (i.e. progression of the study indication) the assessment of causality will usually be 'Not suspected.' The rationale for this guidance is that the symptoms of a lack of efficacy or progression of underlying illness are not caused by the trial drug, they happen in spite of its administration and/or both lack of efficacy and progression of underlying disease can only be evaluated meaningfully by an analysis of cohorts, not on a single participant
3. Its duration (start and end dates) or if the event is ongoing, an outcome of not recovered/not resolved must be reported
4. Whether it constitutes a SAE (see [Section 10.1.2](#) for definition of SAE) and which seriousness criteria have been met
5. Action taken regarding study treatment.

All adverse events must be treated appropriately. Treatment may include one or more of the following:

- Dose not changed
- Dose Reduced/increased

- Drug interrupted/withdrawn
6. Its outcome (i.e. recovery status or whether it was fatal)

Conditions that were already present at the time of informed consent should be recorded in medical history of the participant.

Adverse events (including lab abnormalities that constitute AEs) should be described using a diagnosis whenever possible, rather than individual underlying signs and symptoms.

Adverse event monitoring should be continued for at least 30 days following the last dose of study treatment.

Once an adverse event is detected, it must be followed until its resolution or until it is judged to be permanent (e.g. continuing at the end of the study), and assessment must be made at each visit (or more frequently, if necessary) of any changes in severity, the suspected relationship to the interventions required to treat it, and the outcome.

Information about adverse drug reactions for the investigational drugs can be found in the USPI/applicable labelling information.

Abnormal laboratory values or test results constitute adverse events only if they fulfill at least one of the following criteria:

- they induce clinical signs or symptoms
- they are considered clinically significant
- they require therapy

10.1.2 Serious adverse events

An SAE is defined as any adverse event [appearance of (or worsening of any pre-existing)] undesirable sign(s), symptom(s), or medical condition(s) which meets any one of the following criteria:

- fatal
- life-threatening

Life-threatening in the context of a SAE refers to a reaction in which the participant was at risk of death at the time of the reaction; it does not refer to a reaction that hypothetically might have caused death if it were more severe (please refer to the ICH-E2D Guidelines).

- results in persistent or significant disability/incapacity
- constitutes a congenital anomaly/birth defect
- requires inpatient hospitalization or prolongation of existing hospitalization, unless hospitalization is for:
 - routine treatment or monitoring of the studied indication, not associated with any deterioration in condition
 - elective or pre-planned treatment for a pre-existing condition that is unrelated to the indication under study and has not worsened since signing the informed consent
 - social reasons and respite care in the absence of any deterioration in the participant's general condition

- treatment on an emergency outpatient basis for an event not fulfilling any of the definitions of a SAE given above and not resulting in hospital admission
- is medically significant, e.g. defined as an event that jeopardizes the participant or may require medical or surgical intervention to prevent one of the outcomes listed above

Medical and scientific judgment should be exercised in deciding whether other situations should be considered serious reactions, such as important medical events that might not be immediately life threatening or result in death or hospitalization but might jeopardize the participant or might require intervention to prevent one of the other outcomes listed above. Such events should be considered as “medically significant.” Examples of such events are intensive treatment in an emergency room or at home for allergic bronchospasm, blood dyscrasias, or convulsions that do not result in hospitalization or development of dependency or abuse (please refer to the ICH-E2D Guidelines).

All new malignant neoplasms will be assessed as serious under “medically significant” if other seriousness criteria are not met and the malignant neoplasm is not a disease progression of the study indication.

Any suspected transmission via a medicinal product of an infectious agent is also considered a serious adverse reaction.

All reports of intentional misuse and abuse of the product are also considered serious adverse event irrespective if a clinical event has occurred.

10.1.3 SAE reporting

To ensure participant safety, every SAE, regardless of causality, occurring after the participant has provided informed consent and until 30 days after the last study visit must be reported to Novartis safety within 24 hours of learning of its occurrence. Detailed instructions regarding the submission process and requirements are to be found in the investigator folder provided to each site.

All follow-up information for the SAE including information on complications, progression of the initial SAE and recurrent episodes must be reported as follow-up to the original episode within 24 hours of the investigator receiving the follow-up information. An SAE occurring at a different time interval or otherwise considered completely unrelated to a previously reported one must be reported separately as a new event.

If the SAE is not previously documented in the Package Insert and is thought to be related to the study treatment, a CMO & PS Department associate may urgently require further information from the investigator for health authority reporting. Novartis /Sponsor may need to issue an Investigator Notification (IN) to inform all investigators involved in any study with the same study treatment that this SAE has been reported.

Suspected Unexpected Serious Adverse Reactions (SUSARs) will be collected and reported to the competent authorities and relevant ethics committees in accordance with EU Guidance 2011/C 172/01 or as per national regulatory requirements in participating countries.

Any SAEs experienced after the 30 day safety follow up period should only be reported to Novartis Safety if the investigator suspects a causal relationship to study treatment.

10.1.4 Pregnancy reporting

Pregnancies

If a female trial participant becomes pregnant, the study treatment should be stopped, and the trial participant must be asked to read and sign pregnancy consent form to allow the Study Doctor ask about her pregnancy. To ensure participant safety, each pregnancy occurring after signing the informed consent must be reported to Novartis/Sponsor within 24 hours of learning of its occurrence. The pregnancy should be followed up to determine outcome, including spontaneous or voluntary termination, details of the birth, and the presence or absence of any birth defects, congenital abnormalities, or maternal and/or newborn complications.

Pregnancy should be recorded and reported by the investigator to the Novartis/Sponsor Chief Medical Office and Patient Safety (CMO&PS). Pregnancy follow-up should be recorded on the same form and should include an assessment of the possible relationship to the study treatment any pregnancy outcome. Any SAE experienced during pregnancy must be reported.

Pregnancy outcomes should be collected for the female partners of any males who took study treatment in this study. Consent to report information regarding these pregnancy outcomes should be obtained from the mother.

10.1.5 Reporting of study treatment errors including misuse/abuse

Medication errors are unintentional errors in the prescribing, dispensing, administration or monitoring of a medicine while under the control of a healthcare professional, participant or consumer (EMA definition).

Misuse refers to situations where the medicinal product is intentionally and inappropriately used not in accordance with the protocol.

Abuse corresponds to the persistent or sporadic, intentional excessive use of a medicinal product, which is accompanied by harmful physical or psychological effects.

Study treatment errors and uses outside of what is foreseen in the protocol will be recorded on the appropriate CRF irrespective of whether or not associated with an AE/SAE and reported to Safety only if associated with an SAE. Misuse or abuse will be collected and reported in the safety database irrespective of it being associated with an AE/SAE within 24 hours of Investigator's awareness.

Table 10-1 Guidance for capturing the study treatment errors including misuse/abuse

Treatment error type	Document in Dosing CRF (Yes/No)	Document in AE eCRF	Complete SAE form
Unintentional study treatment error	Yes	Only if associated with an AE	Only if associated with an SAE
Misuse/Abuse	Yes	Yes	Yes, even if not associated with a SAE

For more information on AE and SAE definition and reporting requirements, please see the respective sections.

10.2 Additional Safety Monitoring

10.2.1 Cardiac safety monitoring

In case of QTcF > 500 msec and QTcF prolongation > 60 msec from baseline, please take the following steps:

- Temporarily interrupt study treatment
- Assess the quality of the ECG recording and the QT value and record two additional ECG tracings to confirm the values
- Determine the serum electrolyte levels (in particular hypokalemia, hypomagnesemia and/or hypocalcemia). If abnormal, correct abnormalities before resuming study treatment.
- Review concomitant medication use for other causes for QT prolongation (refer to qt drugs.org for known QT prolonging drugs) and for drugs with the potential to increase the risk of drug exposure of study drugs
- Check the dosing schedule and treatment compliance
- Increase cardiac monitoring as indicated, (consider continuous telemetry monitoring) until the QTcF returns to ≤ 480 msec
- If QTcF is ≤ 480 msec prior to the next dose, continue dosing with another ECG collected 4 hrs post dose
- If QTcF remains > 480 msec prior to the next dose discontinue study treatment for the participant permanently

In case of persistent QTcF > 500 msec and QTcF prolongation > 60 msec from baseline and/or documented new onset arrhythmia (e.g. Torsade de Pointes, Ventricular Tachycardia) or syncope - discontinue treatment for the participant and request evaluation by a cardiologist.

Please refer to [Appendix 1](#) for notable vital signs.

Local practices should be followed to ensure participant safety for Liver and Renal monitoring, in addition below are suggested guidelines for safety monitoring.

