setting. Participants should also be closely monitored for signs and symptoms of hypoglycemia, particularly those who are diabetic and taking anti-diabetic medications. More relevant to the short term administration of HCQ and azithromycin is drug-induced QT interval prolongation and potential pro-arrhythmic effects. To that end, in addition to relevant cardiac exclusion criteria, participants will also need to follow cardiac safety monitoring, with clear guidance on when to discontinue study medications with regard to QTcF changes. In the setting of active COVID-19 disease in the study population, the benefits of short-term treatment in a hospital setting should, in principle outweigh the known potential risks.

Women of child-bearing potential and sexually active males must be informed that taking the study treatment may involve unknown risks to the fetus if pregnancy were to occur during the study, and agree that in order to participate in the study they must adhere to the contraception requirements outlined in the exclusion criteria. If there is any question that the participant will not reliably comply, they should not be entered or continue in the study.

5 Study Population

The study population will consist of approximately 444 male and female adult participants with moderate to severe COVID-19 disease receiving standard of care to be randomized into hydroxychloroquine, hydroxychloroquine plus azithromycin, or placebo in 1:1:1 ratio (148 participants / arm).

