5.2 Exclusion criteria

Participants meeting any of the following criteria are not eligible for inclusion in this study.

1. Use of other investigational drugs within 5 half-lives or 30 days of enrollment whichever is longer
2. Participation in any other clinical trial of an experimental treatment for COVID-19 within 5 half-lives or 30 days of enrollment whichever is longer
3. Expectation of concurrent treatment with other agents with actual or potential direct acting antiviral activity against SARS-CoV-2 during study drug dosing period, including but not limited to oseltamivir and protease inhibitors
4. History of hypersensitivity to any of the study treatments or its excipients or to drugs of similar chemical classes.

5. Requires, in the judgement of the investigator, admission to the intensive care unit (ICU) or mechanical ventilatory support (invasive or non-invasive) prior to the initiation of study drug
(There might be a participant who cannot be admitted to the ICU, even if the participant's condition is severe enough, due to administrative reasons under the current circumstances. This case is also considered under admission to the ICU judged by the investigator)
6. Evidence of cytokine storm syndrome or multi-organ system failure
7. Confirmed co-infection with influenza
8. Creatinine clearance < 45 mL/min or requiring acute renal replacement therapy
9. History or current diagnosis of ECG abnormalities indicating significant risk of safety for participants participating in the study such as:
 - Concomitant clinically significant cardiac arrhythmias, e.g. sustained ventricular tachycardia, and clinically significant second or third degree AV
 - History of familial long QT syndrome or known family history of Torsades de Pointe
 - QTcF > 480 msec (at screening and/or Day 1 at pre-dose) based on the local ECG data
 - Uncorrected electrolyte abnormalities, such as hypokalemia, hypomagnesemia and hypocalcemia
 - Use of agents known to prolong the QT interval within 5 half-lives before screening
10. Any other condition (e.g. known liver disease) which, in the opinion of the investigator, would put the safety of the participant at risk, impede compliance or hinder completion of the study
11. Pregnant or nursing (lactating) women

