2.8.4.1.1 Clinically significant changes in ECG parameters

The number and percentage of participants meeting the Fridericia QTcF interval criteria defined below at any time post-baseline will be summarized by treatment group (new means that the criteria were not met at baseline or was missing at baseline):

Fridericia QTc interval: new > 480 msec, new > 500 msec, change from baseline 30 - 60 msec, change from baseline > 60 msec, New > 500 msec and change from baseline > 60 msec

Summary of clinically significant changes in ECG will be based on ECG recorded locally .

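### For in-hospital dosing, the paired QTcF trigger in Protocol 10.2.1 leaves participants with baselines of 441–480 msec without a numeric rule to interrupt at some readings above 500 msec

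*Protocol*

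**What the plan says.** **Interruption trigger.** Protocol 10.2.1 opens with "In case of QTcF > 500 msec and QTcF prolongation > 60 msec from baseline, please take the following steps". The first step is to interrupt treatment temporarily. The next is "Assess the quality of the ECG recording and the QT value and record two additional ECG tracings to confirm the values". Electrolytes, concomitant drugs, dosing and compliance, and increased cardiac monitoring follow. Dosing may resume at 480 msec or below; otherwise, "If QTcF remains > 480 msec prior to the next dose discontinue study treatment for the participant permanently".

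**Persistent stop.** The same section ends treatment "In case of persistent QTcF > 500 msec and QTcF prolongation > 60 msec from baseline and/or documented new onset arrhythmia", or syncope. The QTcF part repeats the pair.

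**Entry.** Section 5.2 excludes "QTcF > 480 msec (at screening and/or Day 1 at pre-dose) based on the local ECG data", so a baseline of exactly 480 msec is eligible.

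**Early discharge.** Section 6.1.3 allows dosing at home to Day 10 only if QTcF is 480 msec or below at discharge.

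**Safeguards without a QTcF limit.** Section 9.1.1 requires discontinuation where continuing might put the participant at risk, cardiac events included. Section 8.4.4 requires two further ECGs when a tracing raises a possible safety concern, and provides for local review and a central reader. Section 10.2.4 sets up a DMC.

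**Reporting.** SAP 2.8.4.1.1 tabulates "Fridericia QTc interval: new > 480 msec, new > 500 msec, change from baseline 30 - 60 msec", then a change above 60 msec, and then the joint category "New > 500 msec and change from baseline > 60 msec".

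**The concern.** Section 4.5 identifies QT prolongation and possible pro-arrhythmia as the more relevant short-term risk of the two drugs. It says monitoring will come "with clear guidance on when to discontinue study medications with regard to QTcF changes". Because of the pairing, the absolute reading needed to interrupt is highest for those who enter with the longest QTcF.

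More than the interruption depends on the trigger. In 10.2.1 the electrolyte check, the concomitant-drug review, the increased monitoring and the pre-dose check against 480 msec are all steps that follow from it. If the trigger is not met, that section prescribes none of them. ECGs from Day 6 onward are at the investigator's discretion (Table 8-1 and 8.4.4), while predicted peak hydroxychloroquine in blood rises from 525.2 ng/mL on Day 1 to 1128.6 ng/mL on Day 10 (Table 4-2), a ratio of 1128.6/525.2 ≈ 2.1. An inpatient with a reading in the uncovered band on Day 4 could therefore be dosed to Day 10 with no numeric rule requiring either a pause or another ECG.

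**Working it through.** The plan states no figure on this point to reproduce. The check is on the logic of the rule.

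**Inputs.** Let *b* be baseline QTcF and *q* the on-treatment reading, both in msec.
- Trigger: *q* > 500 and *q* − *b* > 60 (Protocol 10.2.1).
- Eligible baselines: *b* ≤ 480 (Protocol 5.2).
- ECG baseline: the Day 1 pre-dose value (SAP 2.1.1.3).
- Resumption: *q* ≤ 480 before the next dose (Protocol 10.2.1).

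**Step 1: reading needed now.** Both conditions hold only when *q* > max(500, *b* + 60).

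**Step 2: uncovered band.** A reading above 500 escapes when *b* + 60 > 500, that is, when *b* > 440. The band runs from just above 500 to *b* + 60, so its width is max(0, *b* − 440).

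**Step 3: rise needed.** Now it is max(60, 500 − *b*). With a trigger of *q* > 500 alone it is 500 − *b*.

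**Step 4: fall needed to resume.** From just above 500 the fall is 500 − 480 = 20. As a share of the rise this is 20/(500 − *b*).

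| Baseline | Reading needed now | Uncovered whole-msec readings | Rise needed now | Rise needed after fix | Share of rise to lose |
|---|---|---|---|---|---|
| 400 | >500 | none | >100 | >100 | 20/100 = 20% |
| 440 | >500 | none | >60 | >60 | 20/60 = 33% |
| 450 | >510 | 501–510 | >60 | >50 | 20/50 = 40% |
| 460 | >520 | 501–520 | >60 | >40 | 20/40 = 50% |
| 470 | >530 | 501–530 | >60 | >30 | 20/30 = 67% |
| 480 | >540 | 501–540 | >60 | >20 | 20/20 = 100% |

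**Step 5: enumeration.** Every whole-msec baseline from 350 to 480 was tested against every reading from 501 to 600. All 40 baselines from 441 to 480 have an uncovered band, and no baseline at or below 440 has one. On a 0.1 msec grid the affected range is 440.1 to 480.0. With *q* > 500 alone, no combination is uncovered.

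**Step 6: two participants at 530 msec.** With a baseline of 460 the rise is 70, so the trigger is met and dosing is interrupted. With a baseline of 475 the rise is 55 and the trigger is 475 + 60 = 535, so it is not met. Under the fix the second participant is also interrupted and must fall 530 − 480 = 50 msec to resume, which is 50/55 = 91% of the rise.

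**Step 7: how far blood levels fall between doses.** On Day 10, predicted Cmin/Cmax = 1012.5/1128.6 = 0.897 (Table 4-2), a fall of about 10%. These are model means under continued t.i.d. dosing. They show only that little drug is lost over one dosing interval.

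**The case against.** **The pairing is deliberate.** It appears twice in 10.2.1, again in the study-level pause example in 9.1.4, and as its own SAP category. Nowhere do the documents say that QTcF above 500 msec alone should stop dosing. This stands: it is a design choice, not a slip. But the documents give no reason for continuing to dose above 500 msec in those who start longer, while the plan refuses to enrol, send home on drug or re-dose above 480 msec. Those are different decisions, but none supports dosing at 540.

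**The reading is not unmanaged.** The 9.1.1 stop and the 8.4.4 repeat ECGs are worded as obligations. Exclusion 9 and Table 6-2 also keep out uncorrected electrolyte abnormalities, significant arrhythmias and other QT-prolonging drugs. This stands as mitigation. The first two depend on someone judging that there is a risk, and the stop for arrhythmia or syncope acts after the event.

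**The guidance is clear.** Section 10.2.1 is explicit. That is fair: the issue is where the line falls, not vagueness.

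**The SAP proves nothing about dosing.** A reader might infer that, because a new value above 500 msec is listed under clinically significant changes, the plan itself accepts that dosing should stop. It does not follow. New values above 480 msec and changes of 30–60 msec sit under the same heading, and on that logic they would stop dosing too. The categories are descriptive.

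**Other remedies exist, and this one has a price.** A lower entry cap, confirmation before interrupting, or closer monitoring in the band are all possible. On the change scale the fix widens the spread: for baselines of 400 to 480, the rise needed goes from 60–100 msec to 20–100 msec. This stands. The deletion is preferred because it leaves eligibility unchanged, keeps the present order of interrupting first and confirming second, and adds no procedure.

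**Conclusion.** The point holds for in-hospital dosing. Participants with baselines of 441–480 msec have an uncovered band above 500 msec, up to 40 msec wide at a baseline of 480. The arithmetic follows directly from 10.2.1 and 5.2. That the line should move is a judgement, resting on the risk named in 4.5 and the absence of any stated reason for dosing above 500 msec. It is a worthwhile, low-cost correction.

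Three stronger readings are not supported:
- That no numeric QTcF rule protects these participants at all. Section 6.1.3 stops treatment above 480 msec at early discharge.
- That dosing would necessarily continue in the band. Section 9.1.1 can require a stop; it does so by judgement, not by a threshold.
- That many participants were exposed to this. The documents give no baseline QTcF distribution, so the share affected cannot be estimated. SAP 1 and 1.1 record a halt for feasibility reasons with 20 randomised, one of them mis-randomised, so at most 20 − 1 = 19 were dosed.

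The practical value lies in the protocol as designed and in any restart or reuse.

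**What to change.** In 10.2.1, delete the condition on prolongation of more than 60 msec from baseline in two places: the interruption trigger and the sentence on persistent QTcF. Any QTcF above 500 msec then starts the steps already listed, in their present order. Confirmation should not become a condition for interrupting. Section 9.1.4 can stay as it is, because its criterion is an example of when a pause may be considered; aligning it is optional.

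Nothing changes for baselines up to 440 msec. The fix adds no rise-only rule: a change from 400 to 495 msec (+95) meets no numeric trigger before or after. Whether it should is a separate decision for the sponsor.

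**Cost.** Participants with baselines of 441–480 msec are interrupted after smaller rises, just over 20 msec at 480. A participant at 480 must return to baseline before the next t.i.d. dose, while drug levels fall little, so many interruptions near that baseline may become permanent. Before Day 5, stopping one drug stops both (9.1.1). These participants stay in the FAS under the treatment-policy strategy (12.4), so the cost is lost exposure, not lost analysis data.
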